APPENDIX C SCHEDULE OF EVENTS

APPENDIX C: SCHEDULE OF EVENTS

Assessment	SCR	Treatment Days			Follow-up Period Days						
TIMEFRAME	Within 28 days of Day 1	D1	D2	D3	D4	D5 (Post Treat Day 1)	D19± 3d (Post Treat Week 2)	D35±3d (Post Treat Week 4)	D64± 3d (Post Treat Week 8)	D94± 3d (Post Treat Week 12)	Unscheduled, Early Termination, SAE ¹
Clinic visit	X	X	X	х	X	X	X	X	X	X	X
Informed Consent	X										
Inclusion / Exclusion	X										
Demographics	X										
Medical & Medication History	X										
Randomization		X									
Physical exam	x										X
Height and Weight ^a	X										
Vital Signs ^b	X	X	X	X	X	X				X	X
Knee X-rays ^c	X										
12-lead ECG ^d	X										
Clinical lab tests ^e	X					X		X		X	X
Pregnancy or FSH Test ^f	X	X									
Application Site Pain, Erythema, Scaling, Pruritus Assessment ^g	X	x	x	x	x	X	X	X	X	X	X
Exploratory Assessment of OA Knee Painh	X	X									
VAS OA Knee Pain Assessment ⁱ		X	X	X	X	x	X	X	X	X	X
WOMAC ^j	X	X				X	X	X	X	X	X
Drug administration		X	X	х	X						
Assess. Of Concomitant Medications ^k	X	X	X	X	X	X	X	X	X	X	X
AE Assessments		X	X	X	X	X	X	X	X	X	X
Study Exit										X	

Schedule of Events (Continued)

- a. Height and weight obtained at Screening.
- b. Vital signs include temperature, blood pressure, heart rate and respiratory rate. Performed at Screening, on Days 1-4 at pre-dose and at 90 minutes (± 5 min) after applying study drug to knees, and at Follow-up on Day 5 and 94.
- c. Knee X-rays of both knees must be obtained unless films/images performed within 6 months before screening. Copies of film and results will be requested.
- d. Standalone 12-lead ECG performed at Screening.
- e. Clinical laboratory tests include (Appendix A):

Hematology: full blood count including RBC, hemoglobin, hematocrit, MCV, MCH, MCHC, WBC, differential white cell count, platelet count (Screening, Day 5, Day 35 and Day 94);

Erythrocyte sedimentation rate (Screening only);

Chemistry: BUN, creatinine, uric acid, bilirubin (total), sodium, potassium, calcium, magnesium, phosphorous (inorganic), chloride, bicarbonate, ALK, AST (SGOT), ALT (SGPT), LDH, GGT, CPK, albumin, total protein, and glucose (Screening, Day 5, Day 35 and Day 94);

IgM RF (Screening only);

Urinalysis: pH, protein, glucose, ketones, bilirubin, blood, urobilinogen, specific gravity, leucocytes (Screening, Day 5, Day 35 and Day 94). Clinically significant abnormal dipstick results will require microscopic analysis.

- f. Serum pregnancy test at Screening and urine pregnancy test at baseline on Day 1 for premenopausal women; FSH (follicle stimulating hormone) test at Screening to confirm postmenopausal status (females only) for up to 2 years after cessation of menses.
- g. Application site pain will be assessed on NRS (0-10); application site erythema/edema will be assessed using modified categorical Draize test (0-3). Scaling and pruritus will also be scored on a similar categorical scale (0-3). Scoring for application site pain (not related to knee pain) will be performed on drug administration Days 1-4 (pre-application [≤ 30 min], and at 15 (± 5 min), 30 (± 5 min), 60 (± 5 min) and 90 minutes (± 5 min) after application) and on Days 5, 19, 35, 64 and 94. Application site skin reactions (erythema, edema, scaling, pruritus) will be assessed on drug administration Days 1-4 at pre-application (≤ 30 min), and at 15 (± 5 min), 30 (± 5 min), 60 (± 5 min) and 90 minutes (± 5 min) after application), and on Days 5 (24 hrs [+/- 4 hrs]), 19 (+/- 3 days), 35 (+/- 3 days), 64 (+/- 3 days) and 94 (+/- 3 days). (Appendix E and Appendix F)
- h. Exploratory assessment of OA knee pain (average daily pain and daily worst pain) at Screening and Day 1 (pre-application [≤30 min]) (Appendix D).
- i. OA Knee pain to be scored on 100 mm VAS scale (Appendix G) pre-treatment (\leq 30 min) on Days 1, 2, 3 and 4 and also on clinic visits at Days 5 (24 hrs [+/- 4 hrs]), 19 (+/- 3 days), 35 (+/- 3 days), 64 (+/- 3 days) and 94 (+/- 3 days).
- j. WOMAC Pain, Stiffness, and Physical Function will be performed at Screening and on Day 1 prior to drug administration (≤ 30 min) and on Days 5 (24 hrs [+/- 4 hrs]), 19 (+/- 3 days), 35 (+/- 3 days), 64 (+/- 3 days) and 94 (+/- 3 days).
- b. Document all medications taken within 90 days of the Screening Visit through Day 94.
- 1. Refer to Section 6.5 for assessments to be completed at time of SAE, early termination or unscheduled visit.

	Vizuri H	ealth	Science	es LLC
CGS-200-1 and CGS-	-200-5 vs.	CGS-	200-0	Vehicle

APPENDIX D

EXPLORATORY ASSESSMENT OF OSTEOARTHRITIS KNEE PAIN

APPENDIX D: EXPLORATORY ASSESSMENT OF OSTEOARTHRITIS KNEE PAIN

Obtained at Screening and pre-dose on Day 1.

On a scale from 0 to 10, with 0 being no pain at all and 10 being the worst pain imaginable, how would you rate your **AVERAGE DAILY PAIN**

0 1 2 3 4 5 6 7 8 9 10 No Worst Pain

Pain Imaginable

On the same scale, how would you rate your DAILY WORST PAIN

0 1 2 3 4 5 6 7 8 9 10

No Worst Pain

Pain Imaginable

APPENDIX E

VAS OA KNEE PAIN

VAS Pain Scale (100 mm)

APPENDIX E: VAS OA Knee Pain

Obtained on Days 1-4: Pre-application (\leq 30 min), and on Days 5, 19, 35, 64 and 94.

pain imaginable

APPENDIX F ASSESSMENT OF BURNING / STINGING PAIN

APPENDIX F: ASSESSMENT OF BURNING / STINGING PAIN

Obtained on Days 1-4: Pre-application (< 30 min), and at 15 (+ 5 min), 30 (+ 5 min), 60 (+ 5 min), and 90 minutes (+ 5 min) after application, and on Days 5, 19, 35, 64 and 94.

Assessment of Burning / Stinging Pain

The question below refers to BURNING OR STINGING PAIN that you may be feeling right now affecting the skin in the area around your knees.

On a scale from 0 to 10, with 0 being no pain at all and 10 being the worst pain imaginable, how would you rate your pain RIGHT NOW in your RIGHT KNEE? (Please circle the number)

0 1 2 3 4 5 6 7 8 9 10 No Worst Pain Pain Imaginable

On a scale from 0 to 10, with 0 being no pain at all and 10 being the worst pain imaginable, how would you rate your pain RIGHT NOW in your LEFT KNEE? (Please circle the number)

0 1 2 3 4 5 6 7 8 9 10 No Worst Pain Pain Imaginable

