	Subjects will receive the Arm-appropriate treatment as a topical application over the frontal aspect of the knee(s) once daily on four consecutive days. The applications will be at the clinic but by the subject under supervision of clinic personnel. Wearing gloves supplied by the clinic staff, the subject will apply the study drug on and around the knee covering a 10cm by 10cm area. The application will be left in place for 60 (up to 65) minutes and then washed off at the clinic by clinic personnel. The amount of Investigational Drug Product to be applied is estimated to be approximately 0.13 mL based on experience in prior studies. Even though both knee(s) will receive application of study test materials, with regard to reduction in WOMAC pain and VAS pain score associated with study treatments, only one knee will be indicated as the "Study Knee". This will be the knee with the highest WOMAC pain score at baseline. If both knees have equal WOMAC pain scores at baseline, then the right knee will be considered the "Study Knee" with regard to WOMAC pain and VAS pain score reduction.	
	The Investigators, all site staff, study subjects and Clinical Research Organization (CRO) personnel (except for the Medical Monitor providing safety oversight) directly involved in the study will remain blinded to the treatment assignment throughout the trial.	
Estimated No. of Subjects:	Total 120 evaluable subjects: 40 subjects will be allocated to each study Arm. An allowance of up to 10 subjects per Arm is to be provided for dropouts whose withdrawal is not due to lack of study drug tolerability).	

Inclusion/Exclusion Criteria:

Inclusion Criteria

The subject must meet all of the following:

- 1. Able to comprehend the informed consent form (ICF) and provide Informed Consent, and capable of complying with all study procedures;
- 2. Male or female, 35 years of age to 75 years;
- 3. OA of at least one knee according to 1986 ACR Classification Criteria;
- 4. OA of at least one knee must be confirmed by tibiofemoral joint radiographs obtained within the past 6 months;
- 5. Rheumatoid factor (RF) negative and Erythrocyte sedimentation rate (ESR) <40 mm/hr;
- 6. Chronic knee pain in at least one knee for > 3 months;
- 7. WOMAC pain score of ≥ 250 (using VAS WOMAC format) at screening, and at baseline, in at least one knee;
- 8. Knee pain score of ≥ 5 on the NRS pain scale at screening, and at baseline, in at least one knee;

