4.0 SELECTION AND WITHDRAWAL OF SUBJECTS

4.1 INCLUSION/ EXCLUSION CRITERIA:

Subjects entering the study must meet all inclusion and exclusion criteria.

4.1.1 Inclusion Criteria:

The subject must meet all of the following:

- 1. Able to comprehend the informed consent form (ICF) and provide Informed Consent, and capable of complying with all study procedures;
- 2. Male or female, 35 years of age to 75 years;
- 3. OA of the at least one knee according to 1986 ACR Classification Criteria;
- 4. OA of at least one knee must be confirmed by tibiofemoral joint radiographs obtained within the past 6 months;
- 5. RF negative and ESR <40 mm/hr;
- 6. Chronic knee pain in at least one knee for > 3 months;
- 7. WOMAC pain score of \geq 250 (using VAS WOMAC format) at screening, and at baseline, in at least one knee;
- 8. Knee pain score of \geq 5 on the NRS pain scale at screening, and at baseline, in at least one knee;
- 9. Knee pain is not potentially due to acute trauma unrelated to OA (no acute traumatic knee injury in medical history);
- 10. No burning-stinging pain, unrelated to subject's knee pain, at intended site of application;
- 11. Knee pain must be greater than pain in any other part of subject's body;
- 12. ACR global functional status I, II, or III (excluding IV);

13. If female, subject must be past childbearing age or otherwise must test negative for pregnancy. Males and females must agree to use effective birth control for at least 30 days after last dose of study drug.

4.1.2 Exclusion Criteria:

The subject must not have any of the following:

- 1. Spontaneously improving or rapidly deteriorating OA of the knee;
- 2. Rheumatoid or psoriatic arthritis, or a form of arthritis (e.g. gout, pseudogout), Paget's disease of bone, or any other disease affecting the joints that are inconsistent with a diagnosis of idiopathic OA;
- 3. Use of topical, oral, or injectable steroids for 1 month prior to screening, or intraarticular-visco-supplementation within 3 months prior to screening;
- 4. Used any capsaicin-containing product on or in the vicinity of the knee within 4 weeks prior to screening;

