- c Application site pain will be assessed on NRS (0-10); application site erythema/edema will be assessed using modified categorical Draize test (0-3). Scaling and pruritus will also be scored on a similar categorical scale (0-3). Scoring for application site pain (not related to knee pain) will be performed on drug administration Days 1-4 (pre-application [≤30 min], and at 15 (± 5 min), 30 (± 5 min), 60 (± 5 min) and 90 minutes (± 5 min) after application) and on Days 5, 20, and 35. Application site skin reactions (erythema, edema, scaling, pruritus) will be assessed on drug administration Days 1-4 (pre-application [≤ 30 min], and at 15 (± 5 min), 30 (± 5 min), 60 (± 5 min) and 90 minutes (± 5 min) after application). (Appendix E and Appendix F).
- d OA knee pain to be scored on 100mm VAS scale pre-treatment (≤ 30 min) on Days 1-4.
- e WOMAC Pain, Stiffness, and Physical Function will be performed on Day 1 prior to drug administration (≤ 30 min).
- f Exploratory assessment of OA knee pain (average daily pain and daily worst pain) (pre-application [≤30 min]) (Appendix F).

"BASELINE" is defined in this study as the WOMAC scores (pain, stiffness, function) and the VAS OA knee pain score recorded within 30 minutes of the first application of study drug.

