6.5 Tolerability Analyses

The primary tolerability endpoint will be tolerability of the formulations on each of Days 1, 2, 3, and 4. On each of these days, subjects will report an NRS score for burning / stinging at the application site pre-treatment and during treatment, and a pre-treatment and during treatment pruritus score. Pre-treatment and during treatment erythema and scaling scores will be recorded by clinic staff assigned to the study. This will be done at 0, 15, 30, 60, and 90 minutes after application to capture time points during treatment and after washing the application site. The score for each of the above tolerability variables will be entered as a value at each assessment time.

For each subject, an area under the curve (AUC) calculation will be performed in 90 minute intervals for each score value. The AUC for a specified time interval will be calculated using the

trapezoidal rule. If we have $n+1$ measurements y_i at times t_i ($i=0, 1, \dots, n$), then the AUC is calculated as $AUC = \frac{1}{2} \sum_{i=0}^{n-1} (t_{i+1} - t_i)(y_i + y_{i+1})$.

For each of Days 1 through 4, the average of AUC from left and right knees will be calculated for each of the tolerability variables. The calculated average of AUC from all the tolerability variables will then be combined and compared between each Active Treatment Arm (CGS-200-5 and CGS-200-1) and the Vehicle Arm (CGS-200-0) using analysis of variance (ANOVA).

A listing will be provided for all the tolerability variables at each visit.

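### The burning/stinging items rely on a lead-in sentence to keep arthritis pain out, and the tolerability AUC is not adjusted for the pre-application score already collected

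*Protocol*

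**What the plan says.** Appendix F is titled as a burning/stinging assessment and opens with "The question below refers to BURNING OR STINGING PAIN that you may be feeling right now affecting the skin" around the knees. Its two scored items, one per knee, then ask "how would you rate your pain RIGHT NOW in your RIGHT KNEE? (Please circle the number" on a 0-10 scale running from no pain to the worst imaginable. Appendix D uses the same scale for arthritis knee pain.

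Table 6-2 footnote c in Protocol 6.2 defines what the score should capture: "Scoring for application site pain (not related to knee pain) will be performed on drug administration Days 1-4". Two inclusion criteria in Protocol 4.1.1 bear on what subjects bring to the form:

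- No. 8: "Knee pain score of ≥ 5 on the NRS pain scale at screening, and at baseline, in at least one knee".
- No. 10: "No burning-stinging pain, unrelated to subject's knee pain, at intended site of application". Burning that belongs to the knee pain is therefore allowed at entry.

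SAP 6.5 says "subjects will report an NRS score for burning / stinging at the application site pre-treatment and during treatment", with timing given as "This will be done at 0, 15, 30, 60, and 90 minutes after application". It continues: "For each subject, an area under the curve (AUC) calculation will be performed in 90 minute intervals for each score value". The trapezoidal rule is applied to the raw scores and the two knees are averaged. BSP, pruritus, erythema and scaling are then combined, and each active arm is compared with vehicle by ANOVA. No pre-application value is subtracted or used as a covariate; it enters only as the first point of the trapezoid.

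**The concern.** The score is meant to exclude knee pain, yet the sentence the subject answers asks for pain in the knee. The only text on the form that narrows it is the lead-in. The form is completed five times a day on four days by people selected for knee pain, so some may answer the item and not the lead-in.

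BSP is the main expected local effect. In VZU00023 it was reported in 100% of CGS-200-5 subjects and 35% of vehicle subjects (Protocol 1.3). It feeds the only planned between-arm tolerability test. Arthritis pain recorded as burning would make that test noisier. Under some conditions it would also make capsaicin look better tolerated than it is. The reading that could reveal or reduce the problem is collected before every application and not used for adjustment.

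**Working it through.** **The plan's own figure.** The only power statement concerns WOMAC pain (SAP 9: n = 40 per arm, difference 63, SD 100). It reproduces: 63 / (100 × √(2/40)) = 2.82, and Φ(2.82 − 1.96) ≈ 80%. No figure is given for the tolerability AUC, so what follows is algebra plus illustrations on assumed inputs, for BSP alone.

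**Step 1: scale.** With readings at 0, 15, 30, 60 and 90 minutes:
- Steady knee pain of 3 with no burning: 3 × 90 = 270.
- Burning of 2.5 throughout and none before: ½ × 15 × 2.5 + 75 × 2.5 = 206.25.

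A mis-scored knee ache can therefore exceed real burning at 2.5, the highest mean reported for CGS-200 in VZU00020.

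**Step 2: what cancels.** A constant background b, added to burning and equal across randomised arms, adds 90b to each arm's mean AUC. The difference changes by 90b − 90b = 0, and only the variance grows.

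**Step 3: what does not cancel.** The mean difference falls only if:
- (a) the 0-10 ceiling is reached;
- (b) subjects report the larger of the two pains; or
- (c) arthritis pain has fallen more on active than on vehicle by Days 2-4.

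**Step 4: illustration with equal arthritis pain.** Assumed: underlying BSP 2.5 active and 0.5 vehicle, SD 1.5, truncated to 0-10; arthritis pain 6.5, SD 1.5. Each cell gives the raw AUC difference, with the standardised difference in brackets.

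| Share mis-scoring | Pains added | Larger pain reported |
|---|---|---|
| 0% | 130 (1.29) | 131 (1.30) |
| 10% | 127 (0.64) | 118 (0.69) |
| 25% | 123 (0.46) | 99 (0.44) |
| 50% | 119 (0.39) | 66 (0.26) |

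When pains add, the mean barely moves (ceiling only) but precision is lost. Subtracting the pre-application score restores the standardised difference to 1.29-1.24 over 10-50% mis-scoring. When the larger pain is reported, it restores it to 1.12-0.64, but the mean difference stays at about 117-66.

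**Step 5: Days 2-4.** With arthritis pain 4.5 on active and 5.5 on vehicle, and pains added, the raw difference falls from 130 to 121, 108 and 84 at 10%, 25% and 50%. The corrected difference stays at 130-128.

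**Step 6: which remedy does what.** Assumed: 25% affected, knee pain averaging 5, larger pain reported, arthritis pain down 75% on active and 30% on vehicle by Day 4. Mean burning is 2.5 and 0.5 from 15 minutes on, so the true difference is ½ × 15 × 2 + 75 × 2 = 165.

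| | Raw | Day 1 covariate | Incremental AUC |
|---|---|---|---|
| Day 1 | 127 | 127 | about 127 |
| Day 4 | 101 | 101 | 151 |

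The covariate is measured before dosing, so randomisation balances it. It cannot shift the expected mean difference, but on Day 1 it lifts the standardised difference from 0.69 to about 1.3.

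The incremental AUC fails on Day 1 for a simple reason. A subject with knee pain 3 and burning 2.5 who reports the larger records 3 throughout. The incremental area is 0, the same as for a vehicle subject with no burning.

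**The case against.** A reader might infer that the form simply asks for knee pain. It does not. The title and the capitalised lead-in both say burning or stinging, the schedule footnotes tell staff the score is not knee pain, and arthritis pain has its own VAS in the same pre-application window. The defect is reliance on the lead-in.

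A reader might also take the Appendix F references for arthritis pain under Tables 6-1 and 6-2 as proof that the forms are confused. They are better read as lettering slips. Appendix C note h cites Appendix D for the same assessment, and note i sends the VAS to Appendix G.

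The strongest inference, that the capsaicin-vehicle difference is shrunk, is not supported as a general statement. Step 2 shows that equal additive spill-over cancels. The Day 2-4 route needs a differential fall in arthritis pain, on which the prior studies disagree. In VZU00021, 42%, 85% and 88% of CGS-200-5 knees met the response criterion on Days 2, 3 and 4, against 20-25% of once-daily vehicle subjects in VZU00022. The vehicle-controlled VZU00023 found essentially equal response.

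Three further objections limit the consequence:
- **The tested outcome is not BSP alone.** Dilution is partial. In an unweighted sum of the four variables, BSP could contribute 10 × 90 = 900 of 900 + 3 × 270 = 1,710. The SAP does not define how they are combined.
- **The entry threshold is indirect.** It need be met in one knee only. Appendix D asks for average and worst daily pain, not current pain, so the 6.5 in step 4 may be high.
- **Tolerability is secondary.** The named BSP endpoint is acceptability to the subject, and SAP 4.5 calls the study exploratory. A standardised difference of 0.66 at 40 per arm still gives about 83% power, although 0.26 gives about 21%. Scores will be listed, so gross spill-over would be visible.

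**Conclusion.** The concern holds in limited form. The scored items depend on a lead-in to exclude arthritis pain, and SAP 6.5 leaves the pre-application score out of the adjustment. Any spill-over adds variance in all arms. It attenuates the mean difference only under conditions (a) to (c).

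No size can be taken from the documents, because the share mis-scoring, current knee pain and the BSP AUC variance are not given. If the larger pain is reported, knee pain averages 2-5 and the step 6 falls apply, the BSP difference shrinks by 5-9% on Day 1 and 5-15% on Day 4 with 10% affected. With 25% affected it shrinks by 11-22% and 14-38%. These figures are for BSP, not the combined AUC that is tested, and the standardised values depend on the assumed SDs.

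A reader might also conclude that statistical adjustment alone repairs the problem. It does so only in part: no analysis in step 6 recovers the Day 1 mean loss. This is a minor, inexpensive improvement to a secondary endpoint.

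**What to change.** 1. **Appendix F.** In each of the two items, name burning or stinging of the skin and tell the subject not to count arthritis pain. This is the only change that addresses attenuation of the Day 1 mean.
2. **SAP 6.5, main comparison.** Replace the ANOVA on the combined AUC with an ANCOVA. The covariate is the matching Day 1 pre-application score, knees averaged and variables combined in the same way. State that its purpose is precision.
3. **SAP 6.5, sensitivity analysis.** Report BSP separately as the incremental AUC (each score minus that day's pre-application score), and tabulate pre-application BSP by arm and day. This addresses bias on Days 2-4. The Day 1 pre-application scores are the cleanest check of spill-over, because no drug has yet been applied.

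**Cost.** One phrase on a form and a few SAP sentences, with no new assessment. The incremental AUC carries the noise of one extra reading. It would also subtract any burning left from a prior application, which the re-application rule in Protocol 5.1.4 limits but does not exclude. The reworded form is slightly less comparable with earlier studies if they used the same one. If forms are already in use, items 2 and 3 remain available but leave the Day 1 mean as it is.

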APPENDIX G ASSESSMENT OF SIGNS AND SYMPTOMS

APPENDIX G: ASSESSMENT OF SIGNS AND SYMPTOMS

Obtained on Days 1-4: Pre-application (\leq 30 min), and at 15 (\pm 5 min), 30 (\pm 5 min), 60 (\pm 5 min), and 90 minutes (\pm 5 min) after application, and on Days 5, 19, 35, 64 and 94.

Assessment of Signs and Symptoms

Right Knee	Left Knee				
Scaling (Circle Response):	Scaling (Circle Response):				
0 = None: no evidence of scaling	0 = None: no evidence of scaling				
1 = Mild: mainly fine scales predominate	1 = Mild: mainly fine scales predominate				
2 = Moderate: somewhat coarser scales	2 = Moderate: somewhat coarser scales				
3 = Severe: coarse, thick scales; rough surface	3 = Severe: coarse, thick scales; rough surface				
Erythema (Circle Response):	Erythema (Circle Response):				
0 = None: no evidence of redness	0 = None: no evidence of redness				
1 = Mild: barely perceptible redness	1 = Mild: barely perceptible redness				
2 = Moderate: obvious redness, possible presence of edema	2 = Moderate: obvious redness, possible presence of edema				
3 = Severe: bright red, possible edema	3 = Severe: bright red, possible edema				
Pruritus (Circle Response):	Pruritus (Circle Response):				
0 = None: no itching	0 = None: no itching				
1 = Mild: occasional, slight itching	1 = Mild: occasional, slight itching				
2 = Moderate: frequent or constant itching; does not disturb sleep	2 = Moderate: frequent or constant itching; does not disturb sleep				
3 = Severe: bothersome itching; disturbs	3 = Severe: bothersome itching; disturbs sleep				

sleep

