3.0 STUDY DESIGN

3.1 OVERALL STUDY DESIGN

This is a multi-center, randomized, double-blind clinical trial to examine the comparative effects on OAKP of CGS-200-1 (1% Capsaicin content) (N=40), CGS-200-5 (5% Capsaicin content) (N=40), and CGS-200 Vehicle (no Capsaicin) (N=40) in subjects with OA of the knees according to the 1986 ACR criteria. Assigned doses will be applied at the clinic for 60 minutes on each of four consecutive days.

Subjects will be randomized to one of the three Arms in this study: CGS-200-1 or CGS-200-5 or CGS-200-0 (Vehicle). All subjects will receive 4 consecutive days of treatment and will then be followed up until the Day 94 visit.

Subjects will receive the study arm appropriate treatment as a topical application over the frontal aspect of the knee(s) once daily on four consecutive days. The applications will be at the clinic but by the subject wearing gloves under supervision of clinic personnel. The application will be left in place for 60 minutes and then washed off at the clinic by clinic personnel. The amount of Investigational Drug Product to be applied is estimated to be approximately 0.13 mL based on experience in prior studies. Even though both knee(s) will receive application of study test materials, with regard to reduction in WOMAC pain and VAS pain score associated with study treatments, only one knee will be indicated as the "Study Knee". This will be the knee with the highest WOMAC pain score at baseline. If both knees have equal WOMAC pain scores at baseline, then the right knee will be considered the "Study Knee" with regard to WOMAC pain and VAS pain score reduction.

Data will be collected from Day 1 through Day 5 and then again on Days 19, 35, 64, and 94 for efficacy, tolerability, and safety measures. The Investigators, all site staff and Clinical Research Organization (CRO) personnel (except the Medical Monitor providing safety oversight) directly involved in the study will remain blinded to the treatment assignment throughout the trial.

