2.2.5 Tolerability Endpoints

The tolerability endpoints (which are secondary in nature) will be:

- (1) The application of study drug does not produce burning-stinging pain (“BSP”) at the application site to a degree that is not acceptable to the subject. BSP at the application site, this will be assessed using a 0 – 10 Numeric Rating Scale (NRS) scale without guideposts. “Acceptability” of BSP will be queried per subject at the end of each application period.
- (2) The application of the study drug does not produce pruritus during application or in the 24 hrs post-application to a degree that is not acceptable to the subject or, if bothersome to the subject, cannot be managed by application of ice or a cold pack or compress.

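### Pruritus grades 2 and 3 are separated by disturbed sleep, which does not fit scores taken in the clinic 15 to 90 minutes after application; the tolerability score is compressed or graded inconsistently

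*Protocol*

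**What the plan says.** **The scale.** Protocol Appendix G defines the upper two pruritus grades as "2 = Moderate: frequent or constant itching; does not disturb sleep" and "3 = Severe: bothersome itching; disturbs sleep". It gives no recall period for the item and no separate anchors for scores taken in the clinic.

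**When it is scored.** On Days 1-4 the form is completed before application and at 15, 30, 60 and 90 minutes "after application, and on Days 5, 19, 35, 64 and 94".

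**Setting.** Protocol 3.1: "Assigned doses will be applied at the clinic for 60 minutes on each of four consecutive days". Under Protocol 5.1.4 subjects apply the product themselves under supervision, and staff cleanse the knees at 60 (up to 65) minutes.

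**Use in the analysis.** SAP 6.5 has subjects report "a pre-treatment and during treatment pruritus score". On timing it says: "This will be done at 0, 15, 30, 60, and 90 minutes after application". Each tolerability variable is turned into a 90-minute trapezoidal AUC and averaged over the two knees. The variables are then combined, and each active arm is compared with vehicle by ANOVA. SAP 4 sets tolerability tests at two-sided 5%.

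**Endpoints that draw on it.** Tolerability endpoint (2) in SAP 2.2.5 begins "The application of the study drug does not produce pruritus during application or in the 24 hrs post-application" and is then qualified by acceptability to the subject and management with cold. Primary safety endpoint (1) in SAP 2.2.3 includes pruritus and sends the reader to Appendix G for scoring. Protocol 2.1 cites Appendix F for the same scoring, but that appendix covers only burning and stinging.

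**The concern.** The step from 2 to 3 should reflect how bad the itching is at the time of scoring. Here it depends on whether sleep was disturbed, and a subject sitting in the clinic minutes after application has had no chance to sleep. Constant itching in that subject fits the grade 2 text however intense it is.

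The grade 3 text also contains a second element, that the itching is bothersome, which such a subject can satisfy. The two halves of the anchor then point to different grades, and nothing tells the subject or the site which half governs.

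The neighbouring items do not have this problem. Burning and stinging in Appendix F is rated 0-10 for the present moment. Grade 3 erythema and scaling rest on what can be seen at the time.

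At stake is how well the trial describes itching while the product is on the skin. Both documents describe an acceptability question for burning-stinging pain at the end of each application, but no matching question for pruritus. The Appendix G item is therefore the only scheduled pruritus score during application. If the worst-affected subjects are mainly in the capsaicin arms, compressing the top of the scale would understate the difference from vehicle on this component. Mixed readings of the anchor would add noise.

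**Working it through.** The plan states no figure for the pruritus score or its AUC, so there is none to reproduce. The check compares the anchors with the timing, then sizes the effect with the SAP's own formula.

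**Inputs**
- Assessment times 0, 15, 30, 60 and 90 minutes (SAP 6.5).
- Scale maxima: pruritus, erythema and scaling 3 (Appendix G); burning-stinging 10 (Appendix F).
- Trapezoidal rule (SAP 6.5): AUC = ½ Σ (t[i+1] − t[i]) (y[i] + y[i+1]).
- Literal reading: the highest pruritus score reachable at 15-90 minutes is 2.

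**Step 1. Which grade applies in the clinic.** Take constant, intense itching at 30 minutes in an awake subject. Grade 2 requires frequent or constant itching without sleep disturbance, and both conditions are met. Grade 3 requires bothersome itching and disturbed sleep; the first is met and the second is not. The whole text gives 2. The label Severe with the word bothersome alone gives 3.

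**Step 2. Pruritus AUC ceiling per knee and day, pre-application score 0.**
- Grade 3 reachable: ½·15·(0+3) + 15·3 + 30·3 + 30·3 = 22.5 + 45 + 90 + 90 = 247.5 score-minutes.
- Capped at 2: ½·15·(0+2) + 15·2 + 30·2 + 30·2 = 15 + 30 + 60 + 60 = 165 score-minutes.
- Difference 82.5, and 82.5 / 247.5 = 33%.

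If all five points sit at the maximum, the figures are 90·3 = 270 and 90·2 = 180, again one third. Averaging over knees leaves the ceiling unchanged when both knees are equally affected.

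**Step 3. Less extreme patterns.** Losing one grade at a single time costs that time's trapezoid weight:

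| Time (min) | Weight (score-minutes) |
|---|---|
| 15 | (15+15)/2 = 15 |
| 30 | (15+30)/2 = 22.5 |
| 60 | (30+30)/2 = 30 |
| 90 | 30/2 = 15 |

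The weights sum to 82.5, which agrees with step 2. The one-third loss needs itching that deserves a 3 at all four times.

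**Step 4. Combined AUC.** The SAP does not define how the variables are combined. Assuming a simple sum and pre-application scores of 0:
- Burning-stinging: ½·15·10 + 15·10 + 30·10 + 30·10 = 825.
- Erythema and scaling: 247.5 each.
- Total with pruritus at 247.5: 825 + 3·247.5 = 1567.5.
- Total with pruritus at 165: 825 + 2·247.5 + 165 = 1485.
- Loss 82.5 / 1567.5 = 5.3%.

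Another way of combining, such as standardising each component first, would give a different share.

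**The case against.** The strongest case on the other side has five parts.

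- **Grade 3 can still be circled.** The form offers the word Severe, the subject reports the pruritus score, and bothersome is part of the anchor. This stands, so a reader should not infer that severe itching during application is impossible to score as 3. What remains is that the outcome depends on which half of the anchor is followed.
- **There is another route for severe itching.** Adverse events are assessed at every visit from Day 1 and graded by RCTC. Item D7 in Protocol Appendix B grades pruritus by intensity, extent and response to treatment, with no sleep criterion, and SAP 7.2.5 tabulates events by highest grade. This stands. A reader might infer that the form would let the trial report no severe pruritus at all, but the documents do not support that. The adverse-event route does not repair the Appendix G score or its AUC.
- **The limit may seldom bind.** In VZU00023, pruritus was reported in 56% of CGS-200-5 subjects and 31% of vehicle subjects (Protocol 1.3). Those are incidences. The same section puts local reactions at RCTC Grade 2 at most. RCTC is a different scale, but this suggests that severe itching may be uncommon.
- **No endpoint has a cut-off at grade 3.** Tolerability endpoint (2) is framed as acceptability, and primary safety endpoint (1) as clinical concern. This stands.
- **Itching need not appear to fall on Days 2-4.** A reader might infer that a pre-dose 3 for a disturbed night would be followed by on-treatment scores limited to 2. Protocol 5.1.4 says a knee still itching from a prior application should not be treated. The pattern would need itching that had resolved yet was scored from recall, and Appendix G states no recall period. The documents do not support it as a general expectation.

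**Conclusion.** The concern holds in a limited form. At 15-90 minutes the line between pruritus 2 and 3 rests on something that cannot be observed in that window. The score is compressed if the anchor is read whole and inconsistent if it is read in part. The documents give no basis for saying which reading will dominate.

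The size is bounded by one third of the pruritus AUC ceiling in the worst case. It is about 5% of the combined ceiling under the simple-sum assumption. Both are ceilings on the scale; neither is an expected bias in the comparison between arms. The result rests on subjects being awake at the in-clinic times, which follows from supervised self-application and self-reported scores, and on the form carrying no instruction beyond Appendix G.

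The reach is the Day 1-4 tolerability score and the pruritus part of primary safety endpoint (1). The WOMAC analyses and the sample size do not use this item. It is worth correcting because the remedy is small.

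**What to change.** Keep the 0-3 scale. For every Day 1-4 score that enters the AUC, including the pre-application score, ask about itching at that moment, as Appendix F does for burning, and define the upper grades by intensity. For example, 2 could be itching that is frequent or constant but tolerable, and 3 constant itching that is hard to tolerate. Keep the sleep wording for Day 5 and later visits only, or move it to a separate overnight item that stays outside the AUC.

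Two alternatives are worse:
- Sleep anchors before application with intensity anchors afterwards would put two different scales inside one trapezoid.
- A 0-10 scale for pruritus would raise its AUC ceiling from 247.5 to 825. Under a simple sum its share of the combined ceiling would go from 247.5 / 1567.5 = 16% to 825 / (825 + 825 + 247.5 + 247.5) = 38%.

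The cost is a wording change to Appendix G and the eCRF item, with notice to sites. No visit or procedure is added and the AUC formula is unchanged. Comparability with earlier studies falls slightly if they used the present anchors, which the documents do not state.
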